### ***13.4.3 Confidentiality***

All records identifying the subject will be kept confidential and, to the extent permitted by the applicable laws and/or regulations, will not be made publicly available.

Subject names will not be supplied to the Sponsor. Only the subject number and initials will be recorded on the case report form (eCRF). If the subject name appears on any other document (e.g., pathologist report) or study materials (e.g., biopsy tissue slides), then that information must be deleted before a copy of the document is supplied to the sponsor. Study data stored on a computer will be stored in accordance with local data protection laws. Subjects will be informed in writing that representatives of the sponsor, IRB, or regulatory authorities may inspect their medical records to verify the information collected, and that all personal information made available for inspection will be handled in strictest confidence and in accordance with local data protection laws.

If the results of the study are published, the subject's identity will remain confidential.

The investigator will maintain a list to enable subjects' records to be identified.

**14 FINAL STUDY REPORT AND PUBLICATION POLICY**

A study report will be prepared by the Sponsor. Independent analysis and/or publication of these data by the investigator(s) or any member of their staff will comply with the terms of the clinical Trial Agreement between the Sponsor, and the investigational site and/or investigator.

The Sponsor will comply with applicable laws regarding the requirements for publication of study results.

**15 APPENDICES**

## APPENDIX 2 MAGIC GVHD ASSESSMENT CRITERIA

GvHD Target Organ Staging				
Stage	Skin a	Liver (bilirubin)	Upper GI	Lower GI (stool output/day)
0	No active (erythematous) GvHD rash	Total serum bilirubin < 34 umol/L (< 2 mg/dL)	No or intermittent b anorexia, nausea or vomiting	Diarrhea <500mL per day or <3 episodes/day for adults c
1	Maculopapular rash < 25% of BSA	Total serum bilirubin 34-50 umol/L (2 to 3 mg/dL)	Persistent anorexia or nausea or vomiting	Diarrhea 500 -999 mL per day or 3-4 episodes per day for adults c
2	Maculopapular rash 25 to 50% of BSA	Total serum bilirubin 51-102umol/L (3.1 to 6 mg/dL)		Diarrhea 1000–1500 mL per day or 5–7 episodes for adults c
3	Maculopapular rash > 50% of BSA	Total serum bilirubin 103-255 umol/L (6.1 to 15 mg/dL)		Diarrhea > 1500 mL per day or > 7 episodes for adults b
4	Generalized erythroderma (> 50% BSA) plus bullous formation and desquamation > 5% of BSA	Total Serum bilirubin > 255umol/L (> 15 mg/dL)		Severe abdominal pain with or without ileus or grossly bloody stools (regardless of stool volume) c

BSA: body surface area, GI: gastro-intestinal tract, GvHD: Graft versus Host Disease MAGIC: Mount Sinai Acute GvHD International Consortium

Overall Grade (based upon most severe target organ involvement)	
0	No stage 1-4 of any organ
I	Stage 1-2 skin without liver, upper GI or lower GI involvement
II	Stage 3 rash and/or stage 1 liver and/or stage 1 upper GI and/or stage 1 lower GI
III	Stage 2-3 liver and/or stage 2-3 lower GI, with stage 0-3 skin and/or stage 0-1 upper GI
IV	Stage 4 skin, liver, or lower GI involvement, with stage 0-1 upper GI

a Use the “rule of nines” or burn chart to determine extent of rash

b To be suggestive for GvHD: anorexia should be accompanied by weight loss, nausea should last at least 3 days, or be accompanied by at least 2 vomiting episodes per day for at least 2 days

c One episode of diarrhea is considered to be about 200 ml for an adult and 3 ml/kg for a child (< 50 kg)

Confidence Level Criteria				
Confidence Level	Pathologic Evidence	Clinician Assessment	Treatment for Acute GvHD	Comments
Confirmed	Unequivocal pathologic evidence of GvHD	GvHD is the etiology for symptoms	Not applicable	GVHD is clearly present even if other etiologies may coexist simultaneously.
Probable	Not required	GvHD most likely etiology for symptoms (as evidenced by treatment being provided)	Yes	GVHD is most likely present, but other etiologies may also explain the symptoms, and there is insufficient evidence to make a confirmed diagnosis.
Possible	Not required	GvHD in differential diagnosis (but no treatment is being provided)	No	GVHD may be present, but other etiologies are favored to the degree that GVHD treatment is not initiated.
Negative	Unequivocal evidence of a diagnosis other than GvHD (e.g. drug rash)	GvHD is no considered as an explanation for the symptoms	No and the symptoms resolve without GvHD treatment	GVHD may be present, but other etiologies are favored to the degree that GVHD treatment is not initiated.

Biopsy Results and Confidence Levels			
Pathology Results	Target Organ Confidence Level		
	Treated as GvHD	Not treated but GvHD in Differential Diagnosis	Not Treated and GvHD Not in Differential Diagnosis
Positive	Confirmed	Confirmed	Confirmed
Equivocal	Probable	Possible	Possible
Nondiagnostic	Probable	Possible	Negative
Non-GvHD etiology	Probable	Negative	Negative

Source: Harris AC, Young R, Devine S, Hogan WJ, Ayuk F, Bunworasate U, et al. International, multicenter standardization of acute graft-versus-host disease clinical data collection: a report from the Mount Sinai Acute GVHD International Consortium. Biol Blood Marrow Transplant: J Am Soc Blood Marrow Transplant. 2016;22:4-10

**APPENDIX 3 MODIFIED KEYSTONE CRITERIA FOR ACUTE GVHD**

GvHD Assessment			
Stage	Skina	Liverb,c	Gutc
0	No GvHD rash	Bilirubin < 2 mg/dL	Diarrhea ≤ 500mL per day No anorexia or persistent nausea or anorexia d
1	Rash < 25% of skin	Bilirubin 2 to 3 mg/dL	Diarrhea > 500 mL per day or persistent nausea or nausea d
2	Rash 25 to 50% of skin	Bilirubin 3.1 to 6 mg/dL	Diarrhea ≥ 1000 mL per day
3	Rash > 50% of skin	Bilirubin 6.1 to 15 mg/dL	Diarrhea ≥ 1500 mL per day
4	Generalized erythroderma with bullous formation	Bilirubin > 15 mg/dL	Severe abdominal pain with or without ileus

Overall Gradee			
I	Stage 1 to 2	None	None
II	Stage 3 or	Stage 1 or	Stage 1
III	–	Stage 2 to 3 or	Stage 2 to 4
IV f	Stage 4 or	Stage 4	–

a The Rules of Nines or burn chart was used to determine the extent of rash. The percent of body surface area involved with rash: head and neck (9%), right arm (9%), left arm (9%), anterior trunk (18%), posterior trunk (18%), right leg (18%), left leg (18%), groin and perineum (1%).

b Range given as total bilirubin.

c For liver or gut, downgrade 1 stage if additional cause of elevated bilirubin or diarrhea had been documented.

d Persistent nausea or anorexia, with histologic evidence of GvHD in the stomach or duodenum.

e Criteria for grading given as minimum degree of organ involvement required to confer that grade.

f Grade IV could have also included lesser organ involvement but with extreme decrease in performance

Source: Przepiorka D, Weisdorf D, Martin P, Klingemann HG, Beatty P, Hows J, Thomas ED. 1994 Consensus Conference on Acute GVHD Grading. Bone Marrow Transplant. 1995 Jun;15(6):825-8.

**APPENDIX 4      NIH DEFINED DIAGNOSTIC OR DISTINCTIVE FEATURES OF  
CHRONIC GVHD 2014**

Organ or Site	Diagnostic (Sufficient to Establish the Diagnosis of Chronic GVHD)	Distinctivea (Seen in Chronic GVHD, but Insufficient Alone to Establish a Diagnosis)	Other Features or Unclassified Entitiesb	Commonc (Seen with Both Acute and Chronic GVHD)
Skin	Poikiloderma Lichen planus-like features Sclerotic features Morphea-like features Lichen sclerosus-like features	Depigmentation Papulosquamous lesions	Sweat impairment Ichthyosis Keratosis pilaris Hypopigmentation Hyperpigmentation	Erythema Maculopapular rash Pruritus
Nails		Dystrophy Longitudinal ridging, splitting, or brittle features Onycholysis Pterygium unguis Nail loss (usually symmetric; affects most nails)		
Scalp and body hair		New onset of scarring or nonscarring scalp alopecia (after recovery from chemoradiotherapy) Loss of body hair, Scaling	Thinning scalp hair, typically patchy, coarse, or dull (not explained by endocrine or other causes) Premature gray hair	
Mouth	Lichen-type changes	Xerostomia Mucocelles Mucosal atrophy Ulcers Pseudomembranes		Gingivitis Mucositis Erythema Pain
Eyes		New onset dry, gritty, or painful eyes Cicatricial conjunctivitis Keratoconjunctivitis sicca Confluent areas of punctate keratopathy	Photophobia Periorbital hyperpigmentation Blepharitis (erythema of the eyelids with edema)	
Genitalia  Females  Males	Lichen planus-like features Lichen sclerosus-like features Vaginal scarring or clitoral/labial agglutination Phimosis or urethral/meatus scarring or stenosis	Erosions Fissures Ulcers		

Organ or Site	Diagnostic (Sufficient to Establish the Diagnosis of Chronic GVHD)	Distinctivea (Seen in Chronic GVHD, but Insufficient Alone to Establish a Diagnosis)	Other Features or Unclassified Entitiesb	Commonc (Seen with Both Acute and Chronic GVHD)
GI tract	Esophageal web Strictures or stenosis in the upper to mid third of the esophagus		Exocrine pancreatic insufficiency	Anorexia Nausea Vomiting Diarrhea Weight loss Failure to thrive (infants and children)
Liver				Total bilirubin, alkaline phosphatase > 2 ULN ALT or AST > 2 ULN
Lung	Bronchiolitis obliterans diagnosed with lung biopsy BOS d	Air trapping and bronchiolitis obliterans on chest CT	Cryptogenic organizing pneumonia Restrictive lung disease e	
Muscles, fascia, joints	Fasciitis Joint stiffness or contractures secondary to sclerosis	Myositis or polymyositis f	Edema Muscle cramps Arthralgia or arthritis	
Hematopoietic and immune			Thrombocytopenia Eosinophilia Lymphopenia Hypo- or hypergammaglobulinemia Autoantibodies (AIHA and ITP)	
Other			Pericardial or pleural effusions Ascites Peripheral neuropathy Nephrotic syndrome Myasthenia gravis Cardiac conduction abnormality or cardiomyopathy	

GVHD indicates graft-versus-host disease; ALT, alanine aminotransferase; AST, aspartate aminotransferase; AIHA, autoimmune hemolytic anemia; ITP, idiopathic thrombocytopenic purpura.

a In all cases, infection, drug effects, malignancy, or other causes must be excluded.

b Can be acknowledged as part of the chronic GvHD manifestations if diagnosis is confirmed.

c Common refers to shared features by both acute and chronic GVHD

d BOS can be diagnostic for lung chronic GVHD only if distinctive sign or symptom present in another organ

e Pulmonary entities under investigation or unclassified.

f Diagnosis of chronic GVHD requires biopsy.

Source: Jagasia, Madan H. et al. National Institutes of Health Consensus Development Project on Criteria for Clinical Trials in Chronic Graft-versus-Host Disease: I. The 2014 Diagnosis and Staging Working Group Report. *Biology of Blood and Marrow Transplantation*, 2015 March; 21 (3):389–401

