**5 STUDY OBJECTIVES AND ENDPOINTS**

Objectives	Endpoints
Primary	

 
To assess the potential efficacy of RGI-2001 in addition to standard of care (SOC) vs SOC for the prevention of aGvHD
 
To characterize the safety and tolerability of 6-weekly IV infusions of RGI-2001 in subjects following alloHSCT
 
	
 
Efficacy: Grades II-IV aGvHD by Day 100 according to the Modified Keystone Criteria (Przepiorka 1995)
 
Safety: Incidence, nature, and severity of treatment-emergent AEs, SAEs, laboratory test values, vital sign measures, and graft failure
 

Secondary	

 
To assess the potential efficacy of RGI-2001 in addition to SOC vs SOC for the prevention of chronic GvHD (cGvHD) according to the secondary endpoints listed
 
To assess the survival of subjects who received RGI-2001 in addition to SOC vs SOC
 
To evaluate the pharmacodynamics effects of weekly dosing of RGI-2001
 
	
 
Grades II-IV aGvHD by Day 180 according to the Modified Keystone Criteria
 
Total and moderate-severe cGvHD at 6 months and 1 year according to 2014 NIH criteria
 
Non-relapse mortality (NRM) rates at Day 100, 6 months and 1 year
 
Disease-free survival (DFS) at 6 months and 1 year
 
GvHD-free, relapse free survival (GRFS)a at 6 months and 1 year
 
Overall survival (OS) at 6 months and 1 year
 
Change from baseline in the percentage of CD4+CD25+CD45RA+ CD127-LO T cells (naive Tregs) on Days 14, 28, 42, 60, 100, 180
 

 
[REDACTED]
 
	
 
[REDACTED]
 

Objectives	Endpoints
	

• [REDACTED]

• [REDACTED]

a A GRFS event includes grade III-IV acute GVHD, chronic GvHD requiring systemic immunosuppressive treatment, disease relapse or progression, or death by any cause.

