### 12.3.1 Analysis of Efficacy Data

The primary endpoint grades II-IV acute GvHD by Day 100 according to the MAGIC criteria will be compared between the study group and CIBMTR controls using logistic regression. The factors that will be considered for adjustment in this model include subject age, gender, donor age, type of donor (MRD, 8/8 URD 7/8 URD), source of allograft, diagnosis (AML, ALL, MDS, MPD including CMML), preparative regimen, GvHD prophylaxis regimen.

Secondary endpoints that will be modeled as binary outcomes will similarly be compared using logistic regression. Secondary endpoints that will be modeled as time-to-event outcomes will be compared using Cox regression.

Potential interactions of RGI-2001 and various factors will be examined by including appropriate factors into regression models.

Given that this is not a randomized study and that the intention is only to assess outcomes for a potential signal, no adjustments will be made for multiple comparisons. As such, a Type II error (or a false negative) is prioritized over a Type I error (or a false positive).

Binary exploratory outcomes will be summarized with proportions, continuous outcomes with means and medians, and time-to-event outcomes with Kaplan-Meier estimates or cumulative incidence estimates for endpoints with competing risks.

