8.1 Acute GVHD

For the primary and secondary endpoints as well as certain exploratory endpoints, Keystone criteria will be used for the determination of the severity of aGVHD. For outcomes at a defined time points, the event time will be defined as the time from the “start date” of first RGI-2001 infusion (i.e., transplant date/Day 0) to the first date aGVHD is diagnosed with Keystone criteria Grades II-IV. The first date of aGVHD will be identified using the following eCRFs:

- Initial report: *aGvHD_d* eCRFs with Question 10 = II-IV (i.e., Keystone Grades)
- Maximum report: *aGvHDmax* eCRFs with Question 1 = II-IV (i.e., Keystone Grades)

The first diagnosis date across the eCRFs meeting the above criteria will be used to define the “event time” for this analysis. Censoring: Subjects who are alive without these events will be censored at the date of completion of the last aGVHD assessment, with follow-up truncated at 180 days. Subjects who die without aGVHD will be treated as competing-risk events. The occurrence of aGVHD as a function of time will be calculated using cumulative-incidence estimates.

As an exploratory outcome, MAGIC criteria will be used for the determination of the severity of aGVHD. Event time will be defined as the time from the “start date” of first RGI-2001 infusion to the first date aGVHD is diagnosed with MAGIC criteria Grades II-IV. The first date will be identified using the following eCRFs:

- Initial report: *aGvHD_d* eCRFs with Question 8 = II-IV (i.e., MAGIC Grades)
- Maximum report: *aGvHDmax* eCRFs with any of the following three categories:
 - Grade II: Stage 3 skin and/or stage 1 liver and/or stage 1 upper GI and/or stage 1 lower GI (questions 3,4,5, and 6 on the eCRF)
 - Grade III: Stage 2-3 liver and/or stage 2-3 lower GI, with stage 0-3 skin and/or stage 0-1 upper GI
 - Grade IV: Stage 4 skin, liver, or lower GI involvement, with stage 0-1 upper GI

The first diagnosis date across the eCRFs meeting the above criteria will be used to define the “event time” for this analysis. Censoring and competing-risk considerations will be the same as with the Keystone criteria (above). The occurrence of aGVHD as a function of time will be calculated using cumulative-incidence estimates.

Similar to above, the analysis will be repeated for Keystone and Magic separately using only Grades III and IV.

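### Appendix 3 misprints the Keystone gut Stage 0 and Stage 1 cells, so upper-GI symptoms without histology have no single grading at the Grade II threshold of the primary endpoint

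*Protocol*

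**What the plan says.** Protocol Section 5 sets the primary efficacy endpoint: "Efficacy: Grades II-IV aGvHD by Day 100 according to the Modified Keystone Criteria". The same criteria define the Day-180 secondary endpoint. SAP Section 8.1 agrees: "Keystone criteria will be used for the determination of the severity of aGVHD". The criteria are printed in Protocol Appendix 3.

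The gut column of Appendix 3 contains:

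- **Stage 0:** diarrhea up to 500 mL per day, then "No anorexia or persistent nausea or anorexia", with marker d after the last word.
- **Stage 1:** "Diarrhea > 500 mL per day or persistent nausea or nausea", with marker d after the last word.
- **Footnote d:** "Persistent nausea or anorexia, with histologic evidence of GvHD in the stomach or duodenum".

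In the overall-grade block, Grade II needs skin Stage 3, or liver Stage 1, or gut Stage 1. Footnote e explains the block: "Criteria for grading given as minimum degree of organ involvement required to confer that grade". Gut Stage 1 with no other organ involved is therefore Grade II.

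SAP Section 8.1 takes the event from the Keystone grade recorded on the eCRF (aGvHD_d Question 10 and aGvHDmax Question 1). It does not rebuild that grade from organ stages.

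**The concern.** The two cells are wrong in their words, not only in their layout. Each names one symptom twice. Stage 1 leaves out anorexia, and neither cell matches the footnote it points to. The histology requirement appears only in that footnote, and the marker sits on the last of two terms, so the page does not settle whether histology is needed for the first term.

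The defect lies on the line between a non-event and an event for the Day-100 primary and Day-180 secondary endpoints. Two careful graders could both follow the table and record different grades for the same patient. Biopsy is not assured: footnote p of the Schedule of Assessments asks sites to document any biopsies obtained and does not mandate one. Appendix 2 prints a neighboring rule for MAGIC upper-GI Stage 1, "Persistent anorexia or nausea or vomiting", and that cell asks for no histology. A grader using both tables could easily carry that reading over.

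**Working it through.** The plan gives no figure to reproduce: the question is one of wording, and the sample-size table is redacted. The check sets the cells against the footnote under each reading of the marker, and then looks at scale.

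**Step 1. Two readings of marker d.**

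- Reading A: d qualifies only the last term. Stage 1 then means persistent nausea (no histology needed), or whatever footnote d describes.
- Reading B: d qualifies the whole symptom phrase. Stage 1 then means persistent nausea or anorexia, with histology.

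**Step 2. Score subjects with no rash, bilirubin below 2 mg/dL and diarrhea of at most 500 mL per day.**

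| Only finding | Reading A | Reading B |
|---|---|---|
| Persistent nausea, with histology | Stage 1, Grade II | Stage 1, Grade II |
| Persistent anorexia, with histology | Stage 1, Grade II (the footnote supplies anorexia) | Stage 1, Grade II |
| Non-persistent nausea, with histology | Not Stage 1 (the footnote requires persistence) | Not Stage 1 |
| Persistent nausea, no histology | **Stage 1, Grade II, event** | **Stage 0, non-event** |
| Anorexia, no histology | **Not Stage 1; Stage 0 also fails, because its first mention of anorexia is unqualified** | **Stage 0 only if d also governs that first mention** |

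The last two rows are the ambiguity. The first three give the same answer either way. A subject with skin Stage 3 or higher, liver Stage 1 or higher, or diarrhea above 500 mL per day is Grade II or higher regardless.

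**Step 3. Scale per subject.** The treated arm is planned at 50 (Protocol Section 12). One reclassified subject moves the rate by 1/50 = 2.0 percentage points, and two by 2/50 = 4.0 points.

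**Step 4. What that could mean for the comparison (illustration only).** Inputs from the Protocol: 50 treated, at least 250 controls (Section 12), one-sided alpha 0.10 (Synopsis), and background Grade II-IV rates of 25% to 70% (Section 4.1.1). Assumptions: power of about 80% before any reclassification, and an unadjusted comparison of two proportions.

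Power = Φ[(d − 1.282 × SE0) / SE1], where d is the control rate pC minus the treated rate pT, p̄ is the pooled rate, SE0 = √[p̄(1 − p̄)(1/50 + 1/250)] and SE1 = √[pT(1 − pT)/50 + pC(1 − pC)/250].

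Example with pC = 0.45 and pT = 0.291:

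- No reclassification: d = 0.159, SE0 = 0.0766, SE1 = 0.0715, power 0.80.
- One treated subject moved to Grade II: pT = 0.311, d = 0.139, SE0 = 0.0766, SE1 = 0.0726, power 0.71.

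Across control rates of 25% to 70%:

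| Treated subjects moved to Grade II | Power, controls unchanged | Power, control rate rises by the same points |
|---|---|---|
| 0 | 0.80 | 0.80 |
| 1 | 0.67-0.72 | 0.78-0.81 |
| 2 | 0.53-0.63 | 0.76-0.82 |

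So a handful of subjects would matter if grading differed between the groups, and would matter little if it did not. The documents do not say which case applies, or whether any subject is affected.

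**The case against.** The strongest reply is that footnote d is part of the table. It supplies the missing anorexia and the histology requirement, and a marker at the end of a short phrase is naturally read as covering the whole phrase. Most of this stands. It settles the first three rows of the scoring table and makes Reading B a fair reading. It does not exclude Reading A, because the marker follows only the last of two nearly identical terms, and it does not tidy Stage 0.

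A reader might infer more than the documents support:

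- **That the table requires unbiopsied nausea to be Grade II and leaves biopsy-proven anorexia ungraded.** The first is one of two readings. The second fails once the footnote is applied.
- **That the primary result is overturned.** The SAP uses the grade recorded on the eCRF. The eCRF wording and completion guide are not in the documents, and the text of Protocol Sections 9.2 and 9.3 was not in the copy I had. Whether the misprint reached data capture is unknown.
- **That the 61.4% nausea rate in Protocol Section 4.6 measures exposure.** It counts treatment-emergent nausea of any cause in the earlier study, not persistent nausea diagnosed as GvHD.
- **That the error cannot cancel against the controls.** Controls come from participating centers through CIBMTR forms, whose grading text is not given, and the comparison has its own SAP. Different grading is possible but not shown.

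It is also fair to say that a larger conflict lies on this boundary. Protocol Section 12.3.1 has the primary endpoint "according to the MAGIC criteria will be compared between the study group and CIBMTR controls using logistic regression", against Keystone in Section 5, the Synopsis and the SAP. That is a separate point, and resolving it in favor of Keystone would leave this misprint in place.

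**Conclusion.** The point holds as a misprinted grading rule at the event threshold. The Stage 0 and Stage 1 gut cells do not match footnote d. As printed, persistent nausea without histology has two defensible gradings, and anorexia without histology has no clean one. Only subjects whose sole qualifying finding is upper-GI symptoms can change status. Each one moves the treated rate by 2 points.

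How many there are, whether events would on balance be added or lost, and whether the controls are graded differently cannot be determined from the documents. The power figures rest on an assumed 80% starting point and an unadjusted test. They show sensitivity and are not an estimate of damage. The point should be corrected because the rule defines the primary endpoint and the remedy is cheap, not because the result is shown to be wrong.

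**What to change.** 1. Reconcile the Stage 0 and Stage 1 gut cells of Appendix 3 with footnote d and the consensus grading source cited under the table. Both cells should name persistent nausea or anorexia, and the marker should clearly cover both symptoms. If the source and footnote d differ, the sponsor should record which governs.
2. Confirm that the completion guide for the aGvHD_d and aGvHDmax eCRFs, and the CIBMTR forms used for controls, grade isolated upper-GI disease the same way. If they differ, say so in the separate comparison SAP.
3. Before the CIBMTR comparison, list every treated subject whose only Grade II criterion is gut Stage 1 by upper-GI symptoms, together with subjects left below Grade II despite such symptoms. Re-check their grades against the corrected wording and document any change.

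Keystone organ stages are already planned for tabulation (SAP Table 14.2.2.3), and biopsies obtained are documented under footnote p of the Schedule of Assessments, so no new data collection is needed. The cost is an appendix correction, an eCRF-guide check and a short listing review. Sample size, alpha and the analysis model do not change.
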